## 2. Background:

1. *State the purpose of the research and describe the related theory/data supporting the intent of the study.*

The purpose of this research is to determine whether nifedipine is effective compared to placebo for delaying delivery sufficient to ensure delivery of corticosteroids and thus reducing preterm birth related morbidity. Nifedipine interferes in calcium transport across cell membranes and is an effective smooth muscle relaxant. We believe that uterine relaxation (tocolysis) from nifedipine may reduce preterm birth.

2. *Describe what is considered standard care (approved and/or customary) for the medical condition being studied, if applicable.*

Although tocolysis is not currently used at Parkland Hospital, it is considered within the standard of care for physicians caring for women in preterm labor.

3. *Explain how the new treatment or procedure may improve standard care, if applicable. Clearly delineate what is considered research study items from the “standard care”.*

If nifedipine is identified as an effective tocolytic for reducing preterm birth, it would be included as part of the standard care for women with preterm labor.

4. *Provide a short statement concerning the status of the drug, drug combination, delivery method, device, or other interventions/concepts to be studied.*

Nifedipine is FDA approved for treatment of angina and hypertension, but it is widely used off-label as a tocolytic for preterm labor.

5. *Indicate whether the research is confirming or an extension of previous work, or whether it is pioneering with little prior information. Include an evaluation of existing knowledge and identify the information gaps that the project intends to address.*

No placebo controlled, randomized trials of nifedipine as an intervention for acute tocolysis of preterm labor (defined as cervical dilatation with contractions) have been reported, therefore, this study will be an important contribution to the medical literature.

6. *Describe published research with animals and/or humans that supports the study hypothesis or objectives. If applicable, include information regarding toxicity. Include a bibliography of key references/citations as applicable.*

### Ex Vivo Data

In human myometrium collected at the time of cesarean section Nitrendipine, a dihydropyridine calcium channel blocker similar to nifedipine, depressed myometrial contractions. (Maigaard, 1986).

### Randomized Trials of Nifedipine

Vis et al (2014) recently reported an unusual study of “randomized women” and “nonrandomized eligible women” with nifedipine tocolysis versus placebo in women between 24 and 34 weeks’ gestation with intact membranes, a short cervix by ultrasound, a negative fetal fibronectin (in theory, low risk of preterm birth) and “symptoms of preterm labor” (symptoms were not further defined). This

was a non-inferiority trial and the authors reported that placebo was not inferior to nifedipine tocolysis. The very small sample size and its very unusual design raise questions about its utility.

No placebo-controlled, randomized trials of nifedipine for acute tocolysis of preterm labor (defined as cervical dilatation and contractions) have been reported. Published studies of nifedipine as a treatment for preterm labor are comparisons to other tocolytic agents (References 8a-aa). These other agents include magnesium sulfate, atosiban and beta-agonist drugs such as ritodrine, none of which have been demonstrated to improve birth outcomes.

## Meta-Analyses of Trials Involving Nifedipine

### *Cochrane Review of Calcium Channel Blockers for Inhibiting Preterm Labor*

The authors included published and unpublished data from 12 trials (1029 women) comparing calcium channel blockers to other tocolytic agents. The relative risk for giving birth within 7 days was decreased (RR 0.76, 95% confidence interval, 0.60-0.97) with nifedipine, and the relative risk for maternal side effects was less (RR 0.32 95% CI, 0.24-0.41). There were fewer adverse neonatal outcomes among patients treated with nifedipine, with the relative risks (95% CI) for RDS, necrotizing enterocolitis & intraventricular hemorrhage being 0.63 (0.46-0.88), 0.21 (0.05-0.96), 0.59 (0.36-0.98).

### *Other Meta-Analyses*

Tsatsaris et al (2001) analyzed 9 randomized trials involving 679 patients comparing nifedipine to beta-agonists. The relative risks (95% confidence intervals) for delaying delivery at least 48 hours, side effects, respiratory distress syndrome and neonatal intensive care unit admission compared to other beta-agonists were 1.52 (1.03-2.24), 0.12 (0.05-0.29), 1.51 (0.63-3.65) and 0.65 (0.43-0.97), respectively. Conde-Agudelo et al (2011) reviewed 26 trials with 2179 women. Compared to beta-agonists, nifedipine significantly reduced risk of delivery within 7 days and before 34 weeks, RDS, necrotizing enterocolitis, IVH, neonatal jaundice and ICU admission. Compared to magnesium sulfate, nifedipine showed no significant differences. Maintenance tocolysis is ineffective.

## Safety

*Reviews of Adverse Outcomes Involving Nifedipine:* In a review of the literature on adverse events following the use of calcium channel blockers like nifedipine for tocolysis, Oei (2006) concluded that: 1) calcium channel blockers should not be combined with intravenous beta-adrenergic agonists (such as ritodrine hydrochloride or terbutaline), 2) intravenous nicardipine or high oral doses of nifedipine should not be used in cases of multiple gestation or when the mother is compromised cardiovascularly, and 3) blood pressure should be monitored and cardiotocography should be recorded when immediate release tablets are used.

Importantly, in the proposed study, only healthy women with **singleton** pregnancies will be consented for participation, sub-lingual (rapid-acting) administration will **not** be used and multiple tocolytics will **not** be employed. Compared to the only FDA approved tocolytic (ritodrine), nifedipine has fewer side effects.

Recently, Xiao et al (2014) reported the effect of magnesium sulfate and nifedipine on the risk of developing pulmonary edema in preterm births: “nifedipine did not increase the odds of developing pulmonary edema [adjusted odds ratio (OR)=1.22 (confidence interval (CI) 0.50, 3.01), P=0.67]”

## Hemodynamic and Metabolic Effects

Papatsonis et al (2003) compared 95 patients randomized to oral nifedipine to 90 patients randomized to intravenous ritodrine. Compared to nifedipine, patients who received ritodrine had significantly lower mean diastolic blood pressures at 24 and 48 hours (65 +/- 12 versus 70 +/- 8,  $p=.001$ , and 65 +/- 12 versus 71 +/- 8,  $p=.004$ , respectively), and significantly higher mean maternal pulses at 24 and 48 hours (105 +/- 17 versus 86 +/- 13,  $p<.0001$ , and 100 +/- 21 versus 85 +/- 12,  $p<.0001$ ). Gucglu et al (2006) studied maternal hemodynamic parameters as well as Doppler waveforms of various fetal structures in 28 women who received nifedipine for preterm labor. The maternal and fetal heart rates were unaffected despite that maternal mean systolic and diastolic blood pressures were lower at 24 hours. Changes in the umbilical artery Doppler measurements were “minimal and not sustained.” Additionally, De Heus et al (2009) reported the effects of the tocolytics atosiban and nifedipine on fetal movements, heart rate and blood flow and concluded: “tocolysis with either atosiban or nifedipine combined with betamethasone administration appears to have no direct fetal adverse effects.”

Recently, Ulubasoglu (2014) reported that there were no statistically significant differences between 24-hour values for the umbilical artery pulsatility index, resistance index (RI), systolic-diastolic (S:D) ratio, right uterine artery measures (pulsatility index, RI, S:D ratio) or left uterine artery measures (RI and S:D ratio), and they concluded that “oral nifedipine is a safe tocolytic agent with no long-term effect on fetomaternal circulation in pregnant women at risk of preterm delivery.”

### **3. Concise Summary of Project:**

- 1. Provide a brief description of the study design. If applicable, describe the treatment arms, use of placebo or comparison drug/device and randomization.*

This will be a randomized, double-blinded, placebo-controlled trial of nifedipine for acute tocolysis (48 hours total duration) of preterm labor in women with singleton gestations between 28-0/7 weeks and 33-6/7 weeks' gestation. After initial monitoring on Labor & Delivery, all women will be admitted to the antepartum ward until approximately 34 weeks' gestation and completion of the full course of corticosteroids, although the provider will determine when it is safe for the patient to be discharged, as is our current routine without tocolysis. Discharge can be affected by whether the patient is considered stable (is she contracting again?), if her cervical exam has changed (if her cervix has increased dilatation, particularly to 4 cm or more, she may not be considered safe for discharge) and if she is receiving any other interventions. We will avoid creating an expectation that by participating in this study, then an exact or particular discharge date is assured.

- 2. Include specific details regarding the study drug(s) being used, including the generic/trade name of the study drug. Include details about drug preparation, packaging, shipping, storage, dispensing, return and destruction. Include details of any dose reductions or dose escalations that may occur including the dose change and duration of transition from one dose to another.*

The generic name is nifedipine which is marketed as Adalat or Procardia as trade names. Generic nifedipine in 20 mg doses will be obtained from a distributor in the United States. The Investigational Drug Service at Parkland Hospital has arranged for the placebo and study drug to be encapsulated by Abrams-Royal Pharmacy, [name]. This pharmacy has experience with drug encapsulation for randomized controlled trials. The Investigational Drug Service at Parkland Hospital is aware that Abrams-Royal Pharmacy will be encapsulating the placebo and study drug. Unused or expired study drug will be returned to the investigational drug service (IDS) pharmacy.

Women who consent to participate in the above study will be randomized by the IDS pharmacy to receive either placebo or a loading dose of nifedipine 20 mg oral capsule, which will then be repeated after 90 minutes if there are persistent contractions. Four hours after the first dose, they will begin nifedipine 20 mg oral capsule every 4 hours for a total duration of 48 hours, up to a maximum of 160

mg the first 24 hour period (120 mg the second 24 hour period), unless delivery occurs sooner. We anticipate that women will remain on Labor & Delivery for monitoring for at least 24 hours prior to consideration of transfer to the high-risk antepartum unit.

- 3. Include information regarding the study drug(s) classification and the mechanism of action, if known.*

Nifedipine is a dihydropyridine class of calcium channel blocker, and are selective for smooth muscle. The dihydropyridines are thought to inhibit uterine myometrial contractions by causing relaxation of the uterine smooth muscle.

- 4. Include a brief description of outcome variables and study endpoints, as appropriate.*

The primary outcome will be delay of delivery until 37 weeks'. Secondary outcomes will include 1) at least 2 doses of betamethasone, 2) delivery within 48 hours' gestation and 3) delivery within 7 days.

- 5. Indicate the maximum number of local subjects to be consented on this protocol, including projected screen failures and early withdrawals. Include subjects who will receive interventions as well as controls, if applicable. For multi-center research, indicate the total sample size for the entire project across all sites.*

Assuming a 50% consent rate, we will be approaching approximately 300 women for consent. Sample size calculations indicate we need 75 women per arm or 150 total women to demonstrate a 33% reduction in preterm birth, based upon 2 prior Randomized Placebo Controlled Trials of tocolysis (magnesium sulfate and ritodrine) performed at Parkland Hospital (Leveno et al, 1986; Cox and Leveno, 1990).

- 6. If the study involves use of existing charts, records, or specimens, specify the maximum number that will be reviewed to compile the data or the sample population necessary to address the research question.*

This is a prospective trial and existing records will not be reviewed.

- 7. Provide the total number of subjects to be studied at this site and approximately how long the study will last.*

It is anticipated that the study will take approximately 4-5 years to consent and study a total of 150 women with preterm labor between 28-0/7 weeks and 33-6/7 weeks.

- 8. Include conditions which would result in the subject exiting the study prior to the expected completion date, such as non-compliance, safety reasons, subject withdrawal of consent, disease progression, etc.*

This is an intent to treat study. Withdrawal of consent would be the only indication for early exit.

#### **4. Study Procedures:**

- 1. Provide a chronological description of all study procedures. If applicable, divide procedures into pilot, screening, and procedures performed at each regular visit. Indicate how many total visits and approximately how long visits will last. For studies that are providing medication(s), give the name(s), dosage, and route of administration. For studies that have more than one arm/part, provide the above information for each.*

Women presenting with symptoms of preterm labor will be assessed using electronic external fetal heart rate and uterine contraction monitoring. Women will receive a baseline and subsequent cervical exams as necessary. If at any time during her evaluation, the woman is dilated to at least 2 cm and has uterine contractions, she will be potentially eligible for study. Women with a singleton gestation between 28-0/7 weeks and 33-6/7 will be approached for consent to participate by Research Nurses employed by the Department of Obstetrics & Gynecology or [name] if a Research Nurse is unavailable. They will be randomized by the IDS Pharmacy into treatment (study drug, nifedipine) or control (placebo) groups.

Study women will receive nifedipine 20 mg or placebo oral capsule followed by a second dose after 90 minutes if there are persistent contractions. Four hours after the initial dose, they will begin nifedipine 20 mg or placebo oral capsule every 4 hours for a total duration of 48 hours, up to a maximum of 160 mg the first 24 hour period (120 mg the second 24 hour period), unless delivery occurs sooner. We anticipate that women will remain on Labor & Delivery for monitoring for at least 24 hours prior to consideration of transfer to the high-risk antepartum unit.

There will be a "HOLD DOSE" parameter in which a dose will be held if an enrolled patient:

- refuses medication
- has heart rate greater than 120

If a dose is held, the nurse will contact the 4th year resident who will ensure [name] is notified.

There will be a "STOPPING RULE" for further individual participation in the study for any of the following criteria: withdrawal of consent, diffuse rash or anaphylaxis reaction to medication (requires confirmation by house officer), hypotension requiring delivery or medication such as ephedrine, or development of any obstetrical outcomes that would normally preclude tocolysis (development of ruptured membranes, development of chorioamnionitis, development of preeclampsia/gestational hypertension, development of bleeding suspicious for abruption, cervical dilatation of 6 cm or more or fetal death), or if a decision is made to either deliver the patient or to use regional anesthesia.

Women without further cervical change after monitoring on Labor and Delivery will be admitted to the antepartum unit for surveillance until approximately 34 weeks' gestation and completion of the full course of corticosteroids, although the provider will determine when it is safe for the patient to be discharged. This is our current practice in such women and is not a study procedure. Discharge can be affected by whether the patient is considered stable (is she contracting again?), if her cervical exam has changed (if her cervix has increased dilatation, particularly to 4 cm or more, she may not be considered safe for discharge) and if she is receiving any other interventions. We will avoid creating an expectation that by participating in this study, then an exact or particular discharge date is assured. Some patients choose to leave earlier (usually due to family obligations) despite the recommendation to stay until 34 weeks' gestation. Women who are discharged from the antepartum unit will be followed-up in the OB Complications Clinic of Parkland Hospital weekly until delivery. This method of outpatient follow-up for patients after discharge from the antepartum unit is also our routine and is not a study specific procedure.

2. *You may include tables, figures and/or flow diagrams if necessary to clarify highly complex studies.*

N/A

3. *Indicate the timing of all study procedures and the anticipated duration of the subject's involvement.*

Study participants involvement in study related procedures will last 48 hours.

4. *As applicable, include the amount and blood to be drawn, tissue samples to be collected, radiation exposure, questionnaires, or other interventions.*

No additional blood, tissue, imaging studies, questionnaires or other interventions are planned.

5. *Note if the subject will be responsible for any research-related costs and estimate the amount of these costs, if applicable.*

This study will be locally funded by the Department of Obstetrics & Gynecology and participants will not be responsible for any research-related costs. Study drug is the only research related cost. All other procedures such as inpatient hospitalization are part of routine care for women with preterm labor and a cervix of 2 cm or more.

6. *If applicable, describe end-of-study procedures, including transition of the subject to alternative care.*

N/A

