#### **11. Subject Safety and Data Monitoring:**

1. *Describe what measures have been taken and/or will be taken to prevent and minimize any risks or discomforts.*

Only singleton pregnancies in women with preterm labor and unruptured membranes will receive either placebo or nifedipine. Multiple tocolytics will not be used. Additionally, intravenous or sublingual (rapid-acting) forms of nifedipine will not be used. Only women with preterm labor at 28-0/7 weeks to 33-6/7 weeks will be included, as women with preterm labor between 24-0/7 weeks and 27-6/7 weeks receive magnesium sulfate for neuroprophylaxis and magnesium sulfate can synergize with nifedipine to block calcium movement through calcium channels. Women with hypotension, tachycardia or significant maternal cardiac disease or hypertension treated with antihypertensives will be excluded at the outset. Women with potential indications for delivery will be excluded. Hold dose parameters and stopping rule for further participation are detailed in Section 4(1) above.

2. *If applicable, discuss provisions for insuring necessary medical or professional intervention in the event of adverse events.*

All study participants will undergo regular vital sign monitoring while on Labor & Delivery and on the antepartum unit. Patients on Labor and Delivery will have continuous electronic fetal monitoring and tocometer evaluation, and patients on the antepartum unit will have daily fetal heart testing. If a maternal or fetal complication is identified, physicians will be immediately available to intervene on behalf of the mother and fetus.

3. Describe the plan for monitoring study data collected to protect subject safety and data integrity. Please review [Guidance on Data and Safety Monitoring Plans](#) for instructions on what information should be provided. If desired, the [DSMP Template](#) may be used and included in your application packet.

See DSMP

4. Note: investigator-initiated studies involving administration of an experimental (i.e. not FDA approved for the indication/population under study) drug, device or intervention **must** submit a Data Safety Monitoring Plan ([DSMP Template](#)) and may be required by the IRB to establish a Data Safety monitoring Board (DSMB).

See DSMP

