### **Summary of Sections 66.0 and 67.0 of the Smart Form for the Data Safety Monitoring Plan and Committee**

*Who comprises the Data Safety Monitoring Committee (DSMC)?*

The DSMC is composed of [name], PhD, Professor and Statistician within the Department of Obstetrics and Gynecology, as well as two faculty physicians from the Department of Obstetrics and Gynecology not participating in the study ([name] and [name]).

*When will the DSMC meet:*

The DSMC will meet at least annually during the projected 4 year duration of the study. Additionally, after accrual of 75 patients (half of the planned 150 patients for recruitment), an interim analysis will be performed.

*What will be analyzed by the DSMC?*

The DSMC will monitor study accrual rate, study attrition including participant withdrawals/dropouts, patterns of AEs and/or unanticipated events, patterns of protocol deviations and/or violations and changes in risk/benefit. Efficacy (positive and negative) as well as possible futility of further study will be examined at the interim analysis. Significance levels for the interim analysis will be altered by the method of Lan-DeMets. Safety will be evaluated at each meeting of the Data Safety and Monitoring Board.

*How will safety be evaluated and what study-specific stopping rules will be used by the DSMC?*

Safety will be evaluated by analyzing situations in which administration of the study drug is stopped according to the "STOPPING RULE" below.

The study would be stopped if nifedipine is found to significantly delay preterm birth, or if a significantly greater number of stillbirths or emergency deliveries due to nonreassuring fetal heart tracing attributable to study drug during the 48 hour period during which the study drug will be administered for acute tocolysis of preterm labor.

*What safety mechanisms are built into the Nifedipine study protocol?*

Apart from the strict inclusion and exclusion criteria and the plan to continue maternal and fetal monitoring for at least 24 hours after beginning the study, the following safety parameters are part of the study protocol:

There will be a "HOLD DOSE" parameter in which a dose will be held if an enrolled patient either refuses medication or has a heart rate greater than 120. If a dose is held, the nurse will contact the 4th year resident who will ensure [name] is notified.

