There will be a "STOPPING RULE" for further individual participation in the study for any of the following criteria: withdrawal of consent, diffuse rash or anaphylaxis reaction to medication (requires confirmation by house officer), hypotension requiring delivery or medication such as ephedrine, or development of any obstetrical outcomes that would normally preclude tocolysis

(development of ruptured membranes, development of chorioamnionitis, development of preeclampsia/gestational hypertension, development of bleeding suspicious for abruption, cervical dilatation of 6 cm or more or fetal death), or if a decision is made to either deliver the patient or to give regional anesthesia.

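### Does the individual stopping rule remove women from the trial, against the intention-to-treat statement?

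*Combined protocol and SAP*

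**What the plan says.** Section 3, item 8 asks what would make a subject leave early. The answer is: "This is an intent to treat study. Withdrawal of consent would be the only indication for early exit".

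Section 4, item 1 gives the hold-dose parameters and then a stopping rule "for further individual participation in the study for any of the following criteria". The list contains drug reactions, hypotension that needs treatment or delivery, several obstetrical developments, and a decision to deliver or to use regional anesthesia. Withdrawal of consent is also on it. The monitoring-plan summary in Section 11 repeats the list, closing with "or if a decision is made to either deliver the patient or to give regional anesthesia". Section 11, item 1 refers back to it: "Hold dose parameters and stopping rule for further participation are detailed in Section 4(1) above".

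The monitoring-plan summary also describes the rule in terms of dosing: "Safety will be evaluated by analyzing situations in which administration of the study drug is stopped according to the", with a pointer to the rule below. In a separate answer it has the DSMC monitor "study attrition including participant withdrawals/dropouts". One of its trial-level stopping conditions concerns excess stillbirths, or emergency deliveries for a nonreassuring fetal heart tracing, "attributable to study drug during the 48 hour period during which the study drug will be administered".

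Section 4, item 3 says: "Study participants involvement in study related procedures will last 48 hours". Section 4, item 1 describes weekly clinic visits until delivery, as routine care, for women discharged from the antepartum unit. Section 8, item 1 takes outcomes from the hospital's routine obstetrical database.

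**The concern.** Two sections seem to give opposite answers on who leaves the trial. If ending participation meant leaving the study, women could go for reasons closely tied to the primary outcome, such as ruptured membranes, advanced dilatation or a decision to deliver. Excluding them would be informative, would break intention to treat, and would cost power. Section 14 names the tests but no analysis population, so it does not settle the matter.

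Two DSMC items also looked exposed. The attrition figure could mean consent withdrawals only, or every woman who met a criterion. And a woman who had already left could be missing from the 48-hour count of stillbirths and emergency deliveries, which bears on stopping the trial.

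**Working it through.** **Count of criteria (Section 4, item 1).** Taking paired terms as one each, and delivery and regional anesthesia as two: (1) consent withdrawn; (2) rash or anaphylaxis; (3) hypotension needing delivery or medication; (4) ruptured membranes; (5) chorioamnionitis; (6) preeclampsia or gestational hypertension; (7) bleeding suggesting abruption; (8) dilatation of 6 cm or more; (9) fetal death; (10) decision to deliver; (11) regional anesthesia. Those not withdrawal of consent: 11 − 1 = 10. Ten is an upper limit for the conflict. A woman about to be delivered is reaching her endpoint, and dosing ends at delivery anyway, so criterion 10 is hardly an early exit.

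**What the rule acts on.**

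| Place | Object of the rule |
|---|---|
| Section 4, item 1 | participation |
| Section 11, item 1 | participation |
| Monitoring summary, rule itself | participation |
| Monitoring summary, safety evaluation | administration of study drug |
| Section 3, item 8 | exit for consent withdrawal only |

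The fourth row explains the third: it refers to the rule by name and says that it stops the drug. The position in Section 4 agrees, since the rule comes straight after the hold-dose parameters. Study procedures last 48 hours, no other interventions are planned (Section 4, item 4), and study drug is the only research cost (Section 4, item 5). Ending active participation in this trial therefore amounts to ending study drug. Follow-up and outcome capture are routine and do not depend on dosing.

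**DSMC items.** Attrition and drug stops appear in different answers of the monitoring summary, and no sentence links them. Safety is assessed by examining the stopping-rule events, so a triggering event is data under review. The trial-level count is tied to the 48-hour period and not to continued dosing. Nothing removes a stopped woman from it.

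**Planning figure.** Inputs from Section 14, item 2: p1 = 0.712, p2 = 0.475, difference d = 0.237, two-sided alpha 5%, power 80%. The mean proportion is p̄ = 0.5935.

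- Uncorrected: n = [1.96·√(2p̄(1−p̄)) + 0.8416·√(p1(1−p1) + p2(1−p2))]² / d² = (1.3615 + 0.5674)² / 0.05617 = 66.2, rounded up to 67.
- With continuity correction: (66.2/4)·[1 + √(1 + 4/(66.2 × 0.237))]² = 74.4, rounded up to 75 per arm, which matches the plan.

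Nothing in this calculation depends on the stopping rule.

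**What the literal reading would cost.** The documents give no stopping rate, so the share lost is assumed, equal in both arms. Power is computed without continuity correction as Φ[(d√n − 1.3615)/0.6741].

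| Share lost | n per arm | Power |
|---|---|---|
| 0% | 75 | 84.7% |
| 5% | 71.25 | 82.8% |
| 10% | 67.5 | 80.7% |
| 20% | 60 | 75.9% |
| 30% | 52.5 | 70.1% |

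These losses arise only if stopped women are dropped from the analysis, which Section 3 rules out.

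**The case for a change.** The best argument for a change is that staff at the bedside work from Section 4, where the loose wording sits, while intention to treat is stated in Section 3 and not in Section 14. The list also includes withdrawal of consent, a true exit, so one phrase seems to mean exit for one criterion and drug stop for ten. And consider a woman stopped for ruptured membranes who then has an emergency delivery within 48 hours of her first dose: the plan does not say in so many words that she is counted. A wording change would cost nothing.

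Part of this stands. The wording is inconsistent in three places, and dropouts are not defined. The rest does not lead to a different analysis. Withdrawal of consent necessarily stops the drug, so it belongs on a list of drug-stopping events; that it also ends participation comes from Section 3. The woman in the example falls within the 48-hour period by which the count is defined. A restatement in Section 14 would repeat what Section 3 settles, and reporting drug stops by criterion and arm is a preference rather than a correction.

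**Conclusion.** This is a clerical slip, and correcting it would change no result or decision. The rule is worded as ending participation in three places and explained as stopping study drug in a fourth. With Section 3, the consistent reading is that stopped women stay in follow-up and in their randomised arm. The analysis set, the sample size of 75 per arm, the DSMC's review and the trial-level stopping conditions are the same whether or not the wording is tidied.

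This rests on two assumptions: that analysts follow the intention-to-treat statement in Section 3, and that delivery outcomes reach the routine database whether or not dosing was completed, as Section 8 describes for women delivered at the hospital. The differing passages can be reconciled as an editorial matter when the document is next revised. No view is taken on the clinical criteria.
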